1.2 Rationale for Conducting the Study

The administration of immunoglobulins via the SC route offers several advantages over IV infusion from a patient's and a physician's perspective. Replacement therapy by rapid SC infusion with a pump was introduced during the late 1980s. Several reports have shown that the SC method is feasible, safe, efficient, cost-effective and highly appreciated by the patients.[11-19]

Self-administration at home with small portable pumps or syringes can easily be learned by the patients, which is another advantage of SC administered immunoglobulins (SCIG). It may remarkably improve the patient's quality of life and compliance as it reduces the frequency of hospitalizations and the need for home care. Administration of IgG via the SC

route provides more stable and well-balanced IgG plasma levels until the end of the treatment interval, in contrast with the peak IgG plasma concentrations attained with IVIG solutions which weaken at the end of dose. When effective IVIG therapy cannot be continued because of the lack of peripheral and central vein access, SCIG might also be an alternative treatment option. Experience has shown that replacement therapy with immunoglobulins is lifesaving. If replacement is started early, and if appropriate amounts are given with sufficient frequency, the cycle of recurrent infections and progressive lung damage can be arrested. Near to normal serum IgG levels can be easily maintained.

Post-dose peak levels of SCIG are reached usually 3–6 days after infusion. It has been shown that after infusion, exogenous IgG is distributed relatively rapidly between plasma and extravascular fluid until approximately half is partitioned in the extravascular space. Therefore, a rapid initial drop in serum IgG is to be expected. Several factors such as the endogenous production, the actual catabolism rate, the underlying disease or inter-patient variability help to explain the wide range observed for terminal half-lives. PK data are required for each new product to ensure that it will not behave differently from existing preparations, in terms of appropriate dose and timing of the infusions.

The rationale for conducting the main clinical study was to investigate the PK characteristics, efficacy, and safety of Octanorm, and to provide guidance on the dosing when switching patients from IV to SC treatment in patients suffering from PI.

The principal purpose of the present (extension) study is to acquire additional safety and tolerability data for patients treated in the medium-to-long term with Octanorm. At the same time, efficacy and quality-of-life (QoL) data will also be acquired.

1.3 Benefit-Risk Statement

Patients with PI need life-long treatment with immunoglobulins. Replacement therapy is expected to achieve protective trough levels of 5–6 g/L.

Standard measures are taken to prevent infections resulting from the use of medicinal products prepared from human blood or plasma. Despite this, when medicinal products prepared from human blood or plasma are administered, the possibility of transmitting infective agents cannot totally be excluded. The virus inactivation methods for Octanorm are described in the Investigator's Brochure.

The safety profile of SCIG is well characterized. For Octanorm, the same type of adverse reactions may be expected. No new or unknown safety problems are expected to emerge for Octanorm, which are not already described in the Investigator's Brochure.

In terms of efficacy, it can reasonably be assumed that Octanorm exhibits the same effectiveness as other SCIG brands.

Results from the main study (SCGAM-01) have been analyzed in Q1 2017 and none of the results or data acquired in that study affect the above benefit–risk assessment.

2 STUDY OBJECTIVES

2.1 Primary Objective

The primary objective of the study is to assess the medium-to-long-term safety and tolerability of Octanorm.

2.2 Secondary Objectives

The secondary objectives of the study are:

- To assess the effect of Octanorm on quality-of-life measures.
- To obtain further data on the efficacy of Octanorm.

3 INVESTIGATIONAL PLAN

3.1 Primary and Secondary Endpoints

3.1.1 Primary Endpoint

There is no single primary endpoint in this present extension study. The primary objective is to assess safety and tolerability in medium-to-long-term administration, and this will be assessed by means of the following variables:

- Occurrence of all treatment-emergent AEs (TEAEs) throughout the entire treatment period starting with the first infusion of IMP.
- Occurrence of temporally associated TEAEs.
- TEAEs by speed of infusion.
- Local injection-site reactions.
- Vital signs (blood pressure, pulse, body temperature, respiratory rate).
- Laboratory parameters (hematology, clinical chemistry and tests for viral safety).

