To provide adequate protection from infection, a serum IgG concentration of >5 g/L following IgG therapy has been recommended. Several retrospective studies and one prospective study, however, have shown that higher serum IgG concentrations, resulting from higher doses of IVIG, are associated with a decreased incidence of infections.[3]

A recent meta-analysis in 16 individual studies of IVIG focused on the diagnosis of pneumonia, the most comparable endpoint, and demonstrated a statistically significant inverse correlation between higher IgG dose and a lower incidence of pneumonia, with a 27% decrease in incidence of pneumonia for every 100 mg/kg increase in dose.[10]

Despite its well-established safety profile, IVIG often leads to undesired symptoms, ranging from mild systemic adverse reactions, such as flushing, fever, muscle aches, tiredness, headache and dizziness, to severe reactions, manifesting as chest pain, tachycardia, and changes in blood pressure, aseptic meningitis, thrombosis or renal failure.[4]

The slower rate of rise towards the peak and the truncation of its height are believed to be responsible for the much lower incidence of systemic adverse events (AEs) with SCIG. This is consistent with observations that many AEs of IVIG infusions are rate-related, and has been repeatedly confirmed.[9]

On the other hand, local reactions at SC injection sites are common. These reactions are rarely severe, and are accepted by most patients. In the meta-analysis by Orange et al. the reporting rate varied from 0.028 to 0.697 per infusion demonstrating that the majority of patients tolerate SCIG well.[3]

Octanorm (also known as Cutaquig), the investigational product (IMP) in this study, is an immunoglobulin preparation from human normal plasma and is manufactured by Octapharma. It contains 16.5% (165 mg/mL) protein. The product is aimed for SC infusion by pump or syringe.

Further information on the IMP can be found in the Investigator's Brochure.

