3.2 Overall Study Design and Plan

The study is a prospective, open-label, non-controlled, single-arm, multicenter phase III safety follow-up study with observation of patients receiving weekly (or bi-weekly at double the weekly dose) doses of Octanorm over a period of up to approximately 4.5 years

The study will be conducted at study sites in the United States that already participated in the SCGAM-01 trial.

Only patients who have completed the main study (SCGAM-01) may be enrolled.

Most patients will migrate directly from the main study into the present extension study. However, some patients are expected to complete the main study before the commencement of the extension study.

Eligible patients who have completed the SCGAM-01 study and were treated with any other commercially available SCIG before the start of the SCGAM-03 study (e.g. owing to a delay in local IRB approval for SCGAM-03) are permitted to enter the SCGAM-03 study.

In the intervening interval they must have received the commercially available SCIG at the approximately same dose which the patient had received in study SCGAM-01. For these patients, the screening visit will be regarded as a fresh start and all screening procedures are to be conducted.

The maximum allowed interval without any IgG treatment before the start of treatment in the SCGAM-03 study is approximately 5 weeks.

Each patient will be treated weekly (or bi-weekly at double the weekly dose) with Octanorm, either at the investigation site (on study visit days) or else at home. Thus the maximum number of study infusions of Octanorm may be up to 234 for each patient (or less if treated bi-weekly). A final examination will be performed 1 week after the last infusion, for both regular and premature termination of the patient's study participation.

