## 8. General Issues for Statistical Analysis

Descriptive summaries will be presented for each of the primary and secondary variables. In general, summaries will be completed for all patients overall and by age group as described in section 4.2.

Continuous, quantitative variable summaries will in general include the number of patients with non-missing values (N), mean, standard deviation, median, minimum and maximum, 1st and 3rd quartile.

Categorical, qualitative variable summaries will include the frequency and percentage of patients who are in the particular category. In general the denominator for the percentage calculation will be based upon the total number of patients in the analysis population unless otherwise specified.

Whenever appropriate, the analyses will be stratified according to the predefined age groups taken from the SCGAM-01 study (2 to <6 |  $\geq 6$  to <12 |  $\geq 12$  to <17 |  $\geq 17$  to  $\leq 75$ ).

Additionally, for primary and secondary endpoints, the following subgroups will be investigated:

- Male vs female subjects
- A different definition of age groups: 2 to < 12, 12 to < 17, 17 to 65, and > 65 years

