### 11.3. Infusion Site Reactions

Infusion Site Reactions are captured on a separate eCRF page; summaries will be prepared for

- Number of patients with infusion site reactions by severity and by type of reaction
- Number of infusions with infusion site reactions by severity, by type of reaction and by week

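### SAP 11.3 counts local injection-site reactions, a primary-objective variable, without an infusion denominator, so the by-week counts move with the number of infusions given as well as with local tolerability

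*Protocol*

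**What the plan says.** Protocol 3.1.1 names "Local injection-site reactions" among the variables that serve the primary objective, and SAP 3.2.1 does the same. The safety analysis sections of the protocol (9.2.3 and 9.2.3.1) give no specific analysis for them. SAP 11.3 gives the only one. It opens with "Infusion Site Reactions are captured on a separate eCRF page; summaries will be prepared for" and then lists two items:

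- At the level of the patient, the item is "Number of patients with infusion site reactions by severity and by type of reaction".
- At the level of the infusion, the item is "Number of infusions with infusion site reactions by severity, by type of reaction and by week".

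Neither item has an infusion denominator, a rate or a confidence limit, and neither is split by dosing regimen. The general rule in SAP 8 reads: "In general the denominator for the percentage calculation will be based upon the total number of patients in the analysis population unless otherwise specified". SAP 8.4 and 11.2 do define a ratio of infusions with an event to infusions, with an upper one-sided 95% limit that allows for intra-patient correlation, but state it only for temporally associated AEs.

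On exposure, Protocol 3.2 says "Each patient will be treated weekly (or bi-weekly at double the weekly dose) with Octanorm". The same section later sets the ceiling on exposure: "Thus the maximum number of study infusions of Octanorm may be up to 234 for each patient (or less if treated bi-weekly"). Protocol 6.2.1 says the number of infusions will depend on when the patient entered. Protocol 4.3.2 and SAP 6.1 rule out replacement of withdrawn patients.

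**The concern.** A count of infusions with a reaction in a given week is the product of two things: how many infusions were given that week and how often an infusion causes a reaction. Only the second is local tolerability. In this study the first will change, because patients leave, are not replaced, have different follow-up and may infuse every second week.

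A by-week table of counts can therefore fall without any gain in tolerability, or stay level while the reaction rate per infusion rises. The second case matters because a bi-weekly infusion carries twice the weekly dose, so the per-infusion rate under that regimen is something a long-term tolerability study should be able to show. The count of patients ever affected has a related weakness: it takes no account of how many infusions each patient received.

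**Working it through.** **Inputs from the documents.** Up to about 4.5 years on study and up to 234 weekly infusions (Protocol 3.2); about 35 patients (Protocol 9.1; SAP 6 plans about 45 in total, including about 10 de novo patients in Canada); literature range for local reactions of 0.028 to 0.697 per infusion (Protocol 1.1).

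**Assumptions, not in the documents.** Per-infusion rates of 0.15 and 0.30; 20 patients remaining; the share on bi-weekly dosing; between-patient correlations of 0.05, 0.1 and 0.2; patients who leave or switch have the same rate as the others.

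**The plan's own figure.** 4.5 × 52 = 234 infusions, which reproduces. Bi-weekly dosing throughout gives 234 / 2 = 117.

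**By-week count.** With n patients on study, a share f on bi-weekly dosing and rate p per infusion, the expected count per week (averaged over two successive weeks) is p × [n(1 − f) + n f / 2].

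| Patients on study | Regimen | Infusions per week | Count at p = 0.30 |
|---|---|---|---|
| 35 | all weekly | 35 | 10.5 |
| 35 | half bi-weekly | 26.25 | 7.9 |
| 35 | all bi-weekly | 17.5 | 5.25 |
| 20 | all weekly | 20 | 6.0 |
| 20 | half bi-weekly | 15 | 4.5 |

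From the first row to the last the count falls by 1 − 4.5/10.5 = 57% with p unchanged. Dividing by a fixed 35 patients, as the SAP 8 default would, does not help: 10.5/35 = 30.0% becomes 4.5/35 = 12.9%. Dividing by infusions given does: 10.5/35 = 4.5/15 = 0.30.

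**A masked increase.** All 35 weekly at 0.15: 35 × 0.15 = 5.25. All 35 bi-weekly at 0.30: 17.5 × 0.30 = 5.25. The per-infusion rate has doubled and the count is the same.

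**Patients ever affected.** If all patients share one rate, the proportion with at least one reaction in m infusions is 1 − (1 − p)^m. At p = 0.028 this is 99.9% for m = 234 and 96.4% for m = 117; at p = 0.697 it is 100%. If rates differ between patients (beta-binomial), the results for m = 234 are:

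| Rate per infusion | Correlation 0.05 | 0.1 | 0.2 |
|---|---|---|---|
| 0.028 | 75% | 57% | 38% |
| 0.10 | 99% | 95% | 82% |
| 0.30 | 100% | 100% | 99% |
| 0.697 | 100% | 100% | 100% |

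The patient count is nearly uninformative about frequency at moderate and high rates, but not at the low end of the cited range once patients differ.

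**The case against.** Several points on the other side have weight.

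- **Saturation.** A reader might infer that nearly every patient will be counted as affected whatever the true rate. That holds across the cited range only if all patients share the same rate. At 0.028 with between-patient variation, the figure is 38% to 75%, which is clearly distinct from 100%. The 234 infusions are also a ceiling, since treatment ends at the earliest of three events (Protocol 6.2.1). At 117 infusions the same row reads 66%, 49% and 33%. Counts of severe or uncommon reaction types need not saturate at all, and SAP 11.3 does break both summaries down by severity and type.
- **A false conclusion.** A reader might infer that the plan would report improving tolerability. The study is descriptive (Protocol 9.2), and nothing instructs anyone to read the weekly counts as a trend. The documents also do not say how many patients will leave or change regimen.
- **A missed benchmark.** The statement that "the reporting rate varied from 0.028 to 0.697 per infusion" comes from the protocol's background review. No comparison with that range is planned, so failing to support one is not a defect.
- **Silence.** SAP 9.4 summarises total infusions, so a crude overall rate could be derived. SAP 14 defers the table layouts. Neither document says whether site reactions also count as AEs in the SAP 11.2 ratio.

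These points remove the stronger readings. They do not supply the denominator. A crude overall rate does not correct a table by week, separates no regimens and has no confidence limit. Deferred layouts are a weak answer for a primary-objective variable when SAP 11.2 writes the same kind of ratio into the plan for another variable.

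**Conclusion.** The point holds in limited form. As written, SAP 11.3 gives counts for a primary-objective variable without the number of infusions behind them, and no other section fills that gap. The dependence of the by-week count on infusions given is arithmetic and holds at any reaction rate. Its size here (10.5 to 4.5, or a doubled rate hidden at 5.25) rests on the assumed rates, attrition and regimen mix.

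For the patient count, the supported statement is only that it is not adjusted for exposure and may saturate at moderate or high rates. This should be corrected before the analysis. It does not affect trial conduct or data collection.

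**What to change.** In SAP 11.3, make the main result the number of infusions with at least one local reaction divided by the number of infusions given. Report it:

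- overall, and by severity and type;
- by exposure period, with the length of the period fixed in advance;
- separately for weekly and bi-weekly infusions, because a pooled rate can shift with the regimen mix when bi-weekly infusions carry double the dose;
- with the number of infusions and of patients at risk in every row, so that any selective withdrawal can be seen;
- with a confidence limit that allows for intra-patient correlation, as in SAP 11.2.

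State also whether site reactions enter the SAP 11.2 ratio. Keep the patient counts as supporting tables.

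The cost is SAP wording and one table. Patients already grade local reactions after each infusion (Protocol 7.3.2), and infusion details are already entered in the eCRF (Protocol 5.7.2).

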3.1.2 Secondary Endpoints

Secondary assessment criteria will be for quality of life and efficacy:

- QoL assessments using the CHQ-PF50 from parent or guardian of patients <14 years of age and the SF-36 Health Survey in patients ≥ 14 years of age.
- Occurrence of serious bacterial infections (SBIs) as defined in [Section 7.2](#).
- The annual rate of all infections of any kind or seriousness.
- Time to resolution of infections.
- Use of antibiotics (number of days and annual rate).

3.2 Overall Study Design and Plan

The study is a prospective, open-label, non-controlled, single-arm, multicenter phase III safety follow-up study with observation of patients receiving weekly (or bi-weekly at double the weekly dose) doses of Octanorm over a period of up to approximately 4.5 years

The study will be conducted at study sites in the United States that already participated in the SCGAM-01 trial.

Only patients who have completed the main study (SCGAM-01) may be enrolled.

Most patients will migrate directly from the main study into the present extension study. However, some patients are expected to complete the main study before the commencement of the extension study.

Eligible patients who have completed the SCGAM-01 study and were treated with any other commercially available SCIG before the start of the SCGAM-03 study (e.g. owing to a delay in local IRB approval for SCGAM-03) are permitted to enter the SCGAM-03 study.

In the intervening interval they must have received the commercially available SCIG at the approximately same dose which the patient had received in study SCGAM-01. For these patients, the screening visit will be regarded as a fresh start and all screening procedures are to be conducted.

The maximum allowed interval without any IgG treatment before the start of treatment in the SCGAM-03 study is approximately 5 weeks.

Each patient will be treated weekly (or bi-weekly at double the weekly dose) with Octanorm, either at the investigation site (on study visit days) or else at home. Thus the maximum number of study infusions of Octanorm may be up to 234 for each patient (or less if treated bi-weekly). A final examination will be performed 1 week after the last infusion, for both regular and premature termination of the patient's study participation.

The study will be ended when Octanorm becomes commercially available in the USA, the sponsor decides to terminate the trial, or December 2020 (whichever comes first). The maximum total duration of the study for an individual patient may be approximately 4.5 years. Study-related procedures will begin only after written informed consent has been obtained from the patient. For patients who are minors, written consent must be obtained from the parents or legal guardians. In addition, when required by the local regulatory authorities or Institutional Review Board (IRB), written assent must be obtained from children and adolescents based upon the age requirements established by those institutions.

The numbers of patients to be enrolled in each age group will follow the numbers emerging from the main study SCGAM-01 and willing and eligible to continue treatment. At the time of preparation of this protocol these numbers are at most:

- ≥ 2 years and < 5 years of age: up to 5 patients
- ≥ 5 years and < 12 years of age: up to 5 patients
- ≥ 12 years and < 16 years of age: up to 10 patients
- ≥ 16 years and ≤ 75 years of age: up to 30 patients
- Total: approximately 35 patients.

An Independent Data Monitoring Committee will continue to periodically review relevant data with emphasis on thromboembolic events (TEEs).

The following interventions and procedures will be performed at predefined time points (see [Section 6.1.2](#)): Drawing of blood samples, determination of body weight, review of the patient's diary, physical examination including vital sign assessments, QoL assessments, assessments of local injection-site reactions, urine sampling, and urine pregnancy tests.

AEs and any changes in concomitant medications will be recorded throughout the study period.

3.3 Discussion of Study Design and Choice of Control Group(s)

3.3.1 Study Design

The designs of the main study SCGAM-01 and of this extension study take into account the FDA's comments and requests included in the clinical hold letter (dated April 27, 2012) for IND 15019 for another SCIG of Octapharma (gammanorm 16.5%).

The study design is also in line with similar study protocols conducted with other SCIG brands.[18,20]

3.3.2 Dosing

The equivalent monthly dose of IgG is usually determined in one of two ways:

- 1:1 dosing, wherein the monthly IVIG dose is split into four equal weekly SCIG infusions;
- AUC dosing, in which the SCIG dose is calculated from PK data to provide a monthly exposure to IgG equivalent to that with IVIG.

The former is common in Europe, while the latter is a requirement of the US FDA for SCIG labelling studies. For AUC dosing, the SCIG dose has been 1.3 or 1.5 times higher than the previous IVIG dose.[3,18,21]

Compared with weekly administration, PK modelling and simulation (completed in May 2017) predicted that administration of Octanorm 16.5% on a biweekly basis at double the weekly dose results in comparable IgG exposure [slightly higher IgG peak (C_{max}) and slightly lower trough (C_{min})].

Therefore, the proposed study design with respect to weekly or bi-weekly dosing is acceptable, having in mind that a corrected DCF will be applied once available. Appropriate dose levels will be maintained by regular monitoring of IgG trough levels.

If the exact DCF is not known, then a value of 1.5 will be used.

The patients will continue receiving the same Octanorm dose (in mg per kg body weight) as was administered at the Week 64 infusion of the SCGAM-01-study.

Dosing will take place on site at study visits, and otherwise at the patient's home, by self-administration or with assistance (relative, care giver etc.).

